## 7. Study Outcomes

### 7.1. Questionnaires + Acceptability Measures

At the baseline clinical visit:

- *Pediatric Medical History Form*
  - Mott Children's Health Center/University of Michigan School of Dentistry Children's Clinic standard form
- *CRF 05 Baseline Parent Questionnaire* (Appendix 10, CRF 05)
- *CRF 06 Child Questionnaire* (Appendix 10, CRF 06)

When scheduled intermediate contact occurs via phone (or in person if presenting to MCHC/UMSOD for other reasons) at 1, 2, 4.5, and 9 months, the following form will be completed by the personnel making the contact, documenting the answers provided by the parent:

- *CRF 07 Intermediate Contact* (Appendix 10, CRF 07)

At recall visits (3 & 6 months, 12 month final recall, plus emergency visits) the parent and patient will complete:

- *CRF 08 Follow-up Parent Questionnaire* (Appendix 10, CRF 08)  
OR
- *CRF 09 6 & 12 Month Parent Questionnaire* (Appendix 10, CRF 09)
- *CRF 06 Child Questionnaire* (Appendix 10, CRF 06)

### 7.2. Clinical Variables

At the baseline visit the study teeth carious lesions will be assessed based on size (mm), dentin color (yellow, brown, black), dentin hardness (soft - any explorer penetration of dentin when very light force is applied or hard – no dentin penetration when using an explorer with very light force), and periapical radiographs (outer/middle/inner third of dentin, major/minor failure criteria). All information will be noted on the respective *CRF Intervention Visit* by the provider prior to treatment. These clinical characteristics will also be recorded for the SDF groups at follow-up visits (as the lesion is exposed clinically). Recall clinical visits will involve assessment of the lesion based on minor and major failure criteria (Table 2). All assessments will be noted on the respective *CRF 3 & 6 Month* (Appendix 10, CRF 10 & 11) or on the *CRF 12 Month* at the patient's 12 month recall (Appendix 10, CRF 12 & 13). Both groups will have periapical radiographs taken at the baseline and 6 and 12 month recalls (and at any other time if deemed clinically necessary). If a radiograph from within 30 days of the visit is available, a radiograph will not be taken at the study visit unless deemed clinically necessary. De-identified clinical photos will also be taken as deemed necessary for research and publication purposes, with parental consent. Length of time and cost for each intervention will be calculated and analyzed for comparison.

**Table 2.** Major and Minor Failure Criteria

	SDF Application	Conventional Restoration
Success	
 
• Caries arrested – dentin feels hard to explorer
 
• No clinical signs or symptoms of pulpal pathology
 
• Tooth exfoliated without major or minor failure
 
	
 
• Restoration appears satisfactory
 
• No clinical signs or symptoms of pulpal pathology
 
• Tooth exfoliated without major or minor failure
 

Minor Failure	
 
• Caries progression – soft dentin, increase in lesion size clinically or radiographically
 
• Reversible pulpitis to be treated without pulpotomy or extraction
 
	
 
• Secondary caries
 
• Restoration fracture or wear requiring repair
 
• Loss of restoration
 
• Reversible pulpitis to be treated without pulpotomy or extraction
 

Major Failure	
 
• Pulpitis requiring pulpotomy or extraction
 
• Abscess formation
 
• Caries progress to the extent that tooth is unrestorable
 
	
 
• Pulpitis requiring pulpotomy or extraction
 
• Abscess formation
 
• Restoration loss leaving tooth unrestorable
 

---------------	---	--

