#### **4.3. Inclusion and Exclusion Criteria**

Eligible children will be identified during a screening at initial presentation. They must fulfill the inclusion criteria which include (Appendix 10, CRF 10):

- Patients must be ages 2-10.
- Presence of at least one active (soft) cavitated carious lesions in the primary dentition, extending into dentin (ICDAS 5 or 6) – Only one tooth will be selected for the study. All others will be restored and monitored according to the American Academy of Pediatric Dentistry (AAPD) guidelines.
- The selected tooth must have a one or two surface lesion (more than 1/3 of the crown of the tooth must be remaining) and must allow for direct application of SDF.
- Study teeth will not have any spontaneous or elicited pain due to caries, tooth mobility, or signs of pulpal infection.
- Selected primary teeth must have an anticipated exfoliation date greater than 12 months away.

Exclusion criteria include children with:

- Hereditary developmental defects such as Amelogenesis Imperfecta and Dentinogenesis Imperfecta
- Severe medical conditions that do not allow the child to be managed in the MCHC/UMSOD clinics
- Known allergy /sensitivity to dental materials being used, including SDF

- Inability of the child to cooperate for treatment, recall examinations, or periapical radiographs.
- Wards of the State, for consenting reasons

After approaching the parent with a brief discussion of the study, determining interest and asking brief pre-screening eligibility questions as approved by the Institutional Review Board (IRB), the informed consent process will occur. Parents will provide both written and verbal consent, and written and verbal assent will also be asked of the children older than age 8 (Appendices 2 &3). Following the informed consent process, full study eligibility criteria will be reviewed with the pediatric dental resident performing the procedure. At time of consent, the parent will also be provided the *Enrollment Information Form* (Appendix 4) as a reminder of important information and frequently asked questions. This form will include information regarding study purpose, duration (12 months, including application/restorative appointment, 3 follow-up visits, and additional follow-up phone calls/contacts), possible resulting appearance, and overall study protocol.

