#### **4.4. Participant Allocation and Blinding**

Subjects enrolled in the study will be randomly assigned to one of the two caries management groups in a 1:1 ratio. Although treatment will be randomly assigned, it will not be possible to blind parents, children, or dentists to the assigned treatment group as the post-operative appearance is likely to differ markedly between groups. In the event treatment for the patient is failing, regardless of the treatment arm assigned, the provider will recommend additional treatment and can withdraw the patient at any time and appropriate reasoning will be recorded. Patients/parents have the right to withdraw from the study at any time and for any reason as well. Additionally their reasoning for withdrawal will be recorded (Appendix 10, CRF 04, 11, 14-17).

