### **5.1. Conventional management of caries**

These children will receive restorative dental care in alignment with the AAPD guidelines, within the confines of the MCHC or UMSOD clinics. This treatment typically includes administration of local anesthesia, placement of rubber dam, caries removal with rotary and hand instruments, and placement of a final restoration. Following completion of the conventional caries management, the provider will complete the *CRF 02 Intervention Visit: Conventional Restoration CRF* (Appendix 10, CRF 02). For both study interventions, fluoride varnish application should not be applied within one week before or after study intervention so that the effects noted will not be confused with known positive effects of topical fluoride varnish applications.

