### **5.2. SDF management of caries**

- The selected tooth with notable decay into dentin will be isolated with cotton rolls.
- No caries removal will be performed, except for food or other obvious debris.
- Tooth will be dried with gauze and SDF solution will be placed on the carious dentin until it is saturated.
- Excess SDF will be blotted dry with a cotton pellet.
- A second application of SDF solution will then be placed to ensure that the entire carious surface is wetted, and excess will again be blotted with a cotton pellet.
- Following the second application of SDF, the area will be isolated for 3 minutes to allow for ample drying before allowing contact with saliva and soft tissues
- Should the SDF come in contact with any soft tissues, soft tissue should immediately be wiped with a saline wipe
- Following completion of the SDF intervention visit, the provider will complete the CRF 03 *Intervention Visit: Silver Diamine Fluoride* CRF (Appendix 10, CRF 03).
- A second application of SDF will be applied at 6 month recall, following the same protocol as noted above (Due to the potential for increased caries arrest rate with a 6 month application).
- Any new carious lesions that develop after the initial treatment will be recorded, and treated using conventional treatment methods and will not be included in the study.
- Following the completion of this study, teeth in the SDF group will be treated according to AAPD guidelines or observed for exfoliation. The parent of an SDF treated child can elect a restoration following AAPD guidelines at the 12 month visit.

Both groups will receive the following, according the standard procedures at the MCHC/UMSOD:

- Oral Health Instruction (OHI) and diet instruction
- Tooth brushing/dentifrice use at home
- Fissure sealants for permanent teeth will be placed if deemed necessary.
- Traditional preventative care at recalls based on AAPD guidelines (Regular recall exams, prophylaxis, scaling, flossing, and fluoride varnish at 6 month recalls will be provided for both treatment arms. Special care will be taken to not apply fluoride varnish directly to the carious lesion which is being treated with SDF.)

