### 7.3. Providers:

Dentists'/pediatric residents' preferences for the 2 treatment options and time needed to complete a baseline visit will be recorded for each of the 2 interventions and logged on the respective *CRF Intervention Visit* (Appendix 10, CRF 02 & 03).

Provider preference of treatment modality cannot be collected through the clinical measurements on the study Case Report Forms. Therefore, collecting this data from the provider in addition to the clinical measurements will show feasibility and likelihood of future use. It would also be of great interest to the dental community.

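### The baseline lesion record is made by the unblinded treating provider on an arm-specific form, and the text does not say that the study tooth is recorded before allocation

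*Combined protocol and SAP*

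**What the plan says.** Section 7.2 lists what is assessed on the study tooth at baseline: lesion size in mm, dentin colour, dentin hardness, and "periapical radiographs (outer/middle/inner third of dentin, major/minor failure criteria". It then says who records this, where and when: "All information will be noted on the respective *CRF Intervention Visit* by the provider prior to treatment".

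The form differs by arm. In section 5.1, "the provider will complete the *CRF 02 Intervention Visit: Conventional Restoration CRF"; in section 5.2, "the provider will complete the CRF 03 *Intervention Visit: Silver Diamine Fluoride* CRF". Section 7.3 confirms the split, with provider data "logged on the respective *CRF Intervention Visit* (Appendix 10, CRF 02 & 03". On blinding, section 4.4 says "it will not be possible to blind parents, children, or dentists to the assigned treatment group".

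On the tooth, section 4.3 requires at least one qualifying lesion and says "Only one tooth will be selected for the study". After consent, "full study eligibility criteria will be reviewed with the pediatric dental resident performing the procedure". The end of section 4.3 then describes a full-mouth ICDAS examination of enrolled children and their random division into two groups. Table 1 in section 6 puts consent, caries assessment, radiographs and intervention in one visit. It lists neither allocation nor the naming of the tooth.

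**The concern.** Randomisation makes the arms comparable in what was fixed before it. A baseline value written down afterwards, by someone who knows the arm and is about to treat, no longer has that protection. A statement that recording precedes treatment is weaker than a statement that it precedes allocation.

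Two things are at stake.

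- **The baseline reading.** In Table 2, growth of the lesion is one way for an SDF tooth to meet minor failure, so the baseline size is the reference for an outcome. The restoration column has no size-change item, so a shifted reading would not cancel between arms.
- **The choice of tooth.** If a child has several qualifying lesions and the choice is not on record before the arm is known, a provider with a view about SDF could, even unintentionally, settle on a different tooth in each arm.

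**Working it through.** The plan gives no figure on this point, so there is none to reproduce. Its sample size (68 before attrition, 98 after) is unaffected. The check is mainly a comparison of the text, followed by two illustrations.

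**Step 1: when and by whom the baseline is recorded.**
- Section 7.2: the provider, before treatment, on the form for the intervention.
- Sections 5.1, 5.2 and 7.3: that form is CRF 02 or CRF 03, according to arm.
- Section 4.4: dentists are not blinded.
- It follows that whoever picks up the form knows the arm.
- Sections 5.1 and 5.2 have the form completed after treatment, while section 7.2 has the baseline entries made before it. A form begun before and finished after treatment satisfies both, and the arm is known throughout.

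**Step 2: whether the tooth is fixed first.**
- Section 4.3 writes the eligibility criteria for the selected tooth, reviews them after consent, and names the ICDAS examination ahead of random division. A qualifying tooth is therefore probably seen first.
- No sentence says that the chosen tooth is recorded before allocation, and no rule covers several qualifying teeth.
- No clear pre-allocation form can be identified from the body text. Section 4.3 cites CRF 10 for eligibility, while section 7.2 cites CRF 10 and 11 for the 3- and 6-month visits.
- Section 4.4 gives a 1:1 ratio but not when or how the allocation is opened.

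**Step 3: which outcomes are reached.**
- *Minor failure, SDF arm:* direct, but only through the size-increase item. Soft dentin, under the same heading in Table 2, is judged at recall without a baseline.
- *Major failure (primary outcome, section 10):* no major-failure criterion in Table 2 compares size with baseline. The link is indirect. Section 6 withdraws a child at minor failure, so a reading that changes who meets minor failure changes who stays under observation for major failure. Separately, the choice among qualifying teeth could affect major failure if deeper or larger lesions carry more risk, which is an assumption.

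**Step 4: illustrations.** All inputs here are assumed; the documents give no lesion counts, reading error or steering rate.

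(a) *Tooth choice.* With two independent, normally distributed lesion sizes, the expected smaller one lies 1/√π = 0.564 SD below the mean. Shift in SDF-arm mean size = 0.564 × (share of children with two qualifying lesions) × (share of those steered to the smaller).
- Share 0.5, steered 0.25: 0.564 × 0.5 × 0.25 = 0.07 SD.
- Share 0.5, steered 1.0: 0.564 × 0.5 × 1.0 = 0.28 SD.

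The documents give no way to turn this into a failure risk.

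(b) *Baseline reading.* For a stable lesion with reading-error SD 0.5 mm at each visit, the difference of two readings has SD 0.5 × √2 = 0.707 mm. Table 2 sets no threshold, so any positive difference is counted as an increase.
- No over-read: P(difference > 0) = 0.50.
- Baseline over-read by 0.25 mm: P(Z > 0.25/0.707) = P(Z > 0.354) = 0.36.
- Baseline over-read by 0.5 mm: P(Z > 0.5/0.707) = P(Z > 0.707) = 0.24.
- Under-reading by 0.5 mm gives the mirror image, 1 − 0.24 = 0.76.

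**The case against.** The strongest reply is that the order of section 4.3 already protects selection. Screening, consent and tooth-level eligibility come before random division, and the requirement that the tooth allow direct SDF application applies to children in both arms, which fits a review made before the arm is known. This largely stands. A reader might infer that eligibility is judged, or a tooth swapped or dropped, after allocation; no section describes that. A reader might also infer that pathology on the baseline film is discovered and acted on once the arm is known. The documents do not say so: signs of pulpal infection are an eligibility matter, and films up to 30 days old may be used, so some may predate the visit.

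Second, section 5 says that each appointment follows a workflow (Appendices 5–8), with forms in Appendices 9 and 10. None was available, and the visit order may be fixed there. This stands as a limit on what can be said about the tooth. It does not remove the body text's placing of baseline findings on arm-specific forms.

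Third, where a value is written does not prove when the lesion was first looked at. That is fair. However, the recorded value is the one used, and section 7.2 ties it to a form chosen by arm.

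Fourth, section 10 plans examiner calibration on colour, hardness and size, using extracted teeth. That addresses reliability, not knowledge of the arm.

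Finally, the illustrative inputs come from no source in the documents. This stands; they show mechanism and direction, not an estimate.

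**Conclusion.** The point holds in limited form. As written, baseline size, colour, hardness and radiograph reading are recorded by the unblinded treating provider on a form chosen by arm, so the record can be influenced by the known allocation. A qualifying tooth is probably identified before random division. The supplied text does not say that it is recorded by then, and it gives no rule for children with several qualifying teeth. The tooth-choice gap therefore matters mainly in those children.

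It would go too far to say that the baseline reading moves the primary outcome directly. It bears directly on one part of SDF minor failure, and on major failure only through withdrawal at minor failure; tooth choice is a separate possible route to major failure.

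Bias is possible, not shown. The 0.07 to 0.28 SD shift and the fall from 50% to 36% or 24% rest wholly on assumed inputs. Confidence is medium, because Appendices 5–10 were not seen. The change is worth making because the trial is open and, under section 11, the residents at each site carry out screening, treatment and recall.

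**What to change.** - Move the baseline lesion and radiograph fields from CRF 02 and CRF 03 to one arm-neutral enrolment form that also names the study tooth and surfaces.
- State in sections 4.3, 4.4 and 7.2 that this form is completed before the allocation is opened, and add both steps to Visit 1 in Table 1.
- Where several teeth qualify, choose by a fixed rule or a random pick.
- State in section 10 that every child is analysed on the tooth named on that form.
- If Appendices 5–10 already fix the tooth before allocation, say so in the protocol body; the baseline fields would still need to move.

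The cost is a form change and a slightly later opening of the allocation within the same visit. No visit, procedure or sample-size change is needed. Section 4.2 mentions slow recruitment and an added site, so enrolment may already have begun. In that case the change applies only to children enrolled afterwards, there will be two baseline procedures in the data, and the date of change should be recorded. Baseline values already written after allocation cannot be made allocation-blind.

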### **4.2. General Outline**

Children, 2-10 years of age will be invited to participate. The original study site is Mott Children's Health Center (MCHC) in Genesee County, Michigan. Following a slow recruitment period, the University of Michigan School of Dentistry (UMSOD) Children's Clinic was added as a second study site. Given the current data in the literature, the combined failure rate for conventional restorative techniques (e.g. compomers) is approximately 29% at one year follow-up, while application of silver diamine fluoride has a failure rate of 63% at one year follow-up, with increased success over time. Although the failure rate of SDF at one-year follow-up seems alarming, as indicated by Zhi, *et al.* it may be possible to increase the success rate with additional applications providing success rates up to 90.1% at 24 months. Using these data,  $\alpha$ -value of 0.05 and a Power set at 80%, the resulting sample size would be 68 (34 per group) as calculated using the software, nQuery (Appendix 1). To account for 30% attrition, the final number needed for the initial study will be 98 (92 for 25% attrition, 86 for 20% attrition). Subjects will be contacted by phone regularly and invited to two intermediate clinic visits (plus a final study visit) to reduce attrition (Table 1). Given a review of the current literature of the few Randomized Controlled Clinical Trials involving SDF worldwide, the majority of this research has been completed with pre-school aged children. Almost all research discusses arresting or prevention of caries in the

primary dentition, as well as prevention of caries on first permanent molars. Due to the strength of the current research, this study will be focused on the primary dentition of children in the U.S. These children and their parents will be approached when presenting for examination/recall/or treatment at Mott Children's Health Center, Flint, MI, or the University of Michigan School of Dentistry Children's Clinic, Ann Arbor, MI. Interested families with children that qualify following screening examination will be provided with an *Informed Consent/Assent* (Appendix 3) and an *Enrollment Information Form* (Appendix 4).

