## **10. Statistical Analysis**

Power of the study will be fixed at 80% ( $\beta=0.20$ ) just as was used in calculation for necessary sample size, with  $\alpha = 0.05$  as the significance level. Data will be entered into SPSS Statistics or

another secured data collection system and data will be analyzed. Information will be stored on a password protected computer using an encrypted file and will be maintained as confidential protected health information (PHI). Examiners will be trained at the start of the study and calibrated on the use of the ICDAS criteria, and on the clinical outcome variables using extracted teeth to determine intra and inter-examiner reliability (dentin color, dentin hardness, and lesion size in mm), which will be measured with kappa statistics. A Chi-square test will be applied to determine if there is a difference in distribution of variables such as age, gender, brushing habits, fluoride exposure, etc. Chi-square tests will also be used to determine differences in dropout rates, failure rates, patient satisfaction/acceptance, and overall cost. The primary outcome, the proportion of children reporting major failures during the 12 month follow up period, will be analyzed using a mixed model with a binomial error structure. We will also analyze minor failures in a similar manner. The dependent variables will be a binary indicator of major failure, with differences between study treatments fitted as fixed effects. Estimates of the relative risk of major failure in the two groups will be presented in the form of odds ratios and associated 95% confidence intervals. Within this framework we will be able to estimate:

1. The mean difference between groups at the end of the follow up period;
2. The mean difference between groups across the whole of the follow up period; and
3. The difference in the rate of change of the outcome across the follow up period

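### One of the three major-failure criteria in Table 2 counts an unrestorable tooth only through a different cause in each arm, so that component of the primary outcome is not comparable between arms

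*Combined protocol and SAP*

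**What the plan says.** Section 10 names the primary outcome as "the proportion of children reporting major failures during the 12 month follow up period". Table 2 in section 7.2 defines major failure separately for each arm, with three lines per column.

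- Lines one and two have the same wording in both columns: "Pulpitis requiring pulpotomy or extraction" and "Abscess formation".
- Line three for SDF is "Caries progress to the extent that tooth is unrestorable".
- Line three for conventional restoration is "Restoration loss leaving tooth unrestorable".

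In the minor-failure row, the conventional column lists "Secondary caries" with no limit on severity, and also lists fracture or wear of the restoration and its loss. The SDF column lists caries progression. Section 6 says that a child with either grade of failure is withdrawn, the tooth treated and the outcome recorded as a failure. Nowhere does the plan say that an unrestorable tooth is a major failure whatever the cause.

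**The concern.** The third line describes the same end state in both columns, a tooth that can no longer be restored, but counts it only when it arises by the route named for that arm. Where the route is not the named one, two teeth in the same condition can receive different scores because of the treatment assigned. The odds ratio for major failure would then mix a treatment effect with an effect of the definition, and neither a larger sample nor longer follow-up would separate them.

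The major/minor line is final once applied, because section 6 withdraws the child at either grade. It is also applied by dentists who know the arm (section 4.4). The calibration in sections 10 and 11 covers ICDAS, dentin color and hardness, lesion size and SDF technique; restorability is not listed.

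**Working it through.** **1. Applying Table 2 as written.** Take teeth that are unrestorable but have no abscess and no pulpitis that meets the first line.

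| Tooth | Major line met? | Score |
|---|---|---|
| SDF, destroyed by caries progression | Yes, line three | Major |
| Conventional, destroyed by secondary caries, restoration in place | None | Minor |
| Conventional, fracture, restoration not lost | None | Minor |
| Conventional, restoration lost | Yes, line three | Major |
| SDF, caries arrested, crown broken down | None | Not major |

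The minor rows lead to the major rows unevenly. SDF caries progression and conventional loss of the restoration each have a major counterpart. Conventional secondary caries and restoration fracture have none.

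**2. The plan's own figure.** Section 4.2 uses 29% against 63% failure, alpha 0.05 (two-sided assumed) and 80% power. The mean proportion is (0.29 + 0.63)/2 = 0.46.

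n = [1.960·√(2·0.46·0.54) + 0.842·√(0.29·0.71 + 0.63·0.37)]² / 0.34² = (1.381 + 0.558)² / 0.1156 ≈ 32.5, so 33 per arm against 34 stated. Power at 34 is 0.818.

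Attrition: 34/0.70, 34/0.75 and 34/0.80, rounded up and doubled, give 98, 92 and 86, as stated. The sample size reproduces and does not depend on this point: on the conventional side it rests on "the combined failure rate for conventional restorative techniques (e.g. compomers) is approximately 29% at one year follow-up", not on major failure alone.

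**3. Illustration of size (assumed rates).** The plan gives no major-failure rate and no rate for the unrestorable component. Assume the same true risk p in both arms, and that a share s of conventional major events is missed because the cause is not listed. The recorded conventional risk is q = p(1 − s), and

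OR (SDF vs conventional) = [p/(1 − p)] / [q/(1 − q)].

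| p | s = 10% | s = 25% | s = 50% |
|---|---|---|---|
| 5% | 1.12 | 1.35 | 2.05 |
| 10% | 1.12 | 1.37 | 2.11 |
| 20% | 1.14 | 1.42 | 2.25 |

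With 34 per arm, the conventional events lost are 34·p·s, from 34 × 0.05 × 0.10 ≈ 0.2 to 34 × 0.20 × 0.50 = 3.4.

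If the loss fell only in the SDF arm, the ratios would be the reciprocals, from 1/1.12 ≈ 0.90 to 1/2.25 ≈ 0.44. If the same share were lost in both arms, the ratio would be 1.00.

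**4. One event.** At 10%, 34 per arm gives about 3 events. Moving one conventional event to minor makes it 3 against 2: (3/31)/(2/32) = 1.55. The standard error of the log odds ratio is √(1/3 + 1/31 + 1/2 + 1/32) = 0.947, so the 95% interval is about 0.24 to 9.9.

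**The case against.** A reader might infer that the primary outcome as a whole is a different event in the two arms. The documents do not support that. Two of the three criteria match word for word, and the third shares its end state. Some arm-specific wording is also natural, since an SDF tooth has no restoration to lose.

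The affected group is narrow. In the conventional arm the tooth must be unrestorable, with no abscess, no pulpitis that meets the first line, and the restoration not lost. Study teeth start with one- or two-surface lesions and more than a third of the crown remaining (section 4.3). They are examined at 3, 6 and 12 months, and a minor failure leads to treatment and withdrawal (section 6), so much secondary caries would be dealt with before it reached this state. Table 2 can also be read as a hierarchy in which minor findings become major when severe. That reading fits loss of the restoration and SDF caries progression, which have a written major counterpart, but secondary caries and restoration fracture have none.

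A conventional tooth scored minor is not lost to the trial. Minor failures get a parallel analysis, and section 10 also compares failure rates by chi-square. That preserves the total but not the primary comparison: the same tooth lowers one count and raises the other.

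What stands of the objection is that the effect may be small and its sign is unknown. The gap in the definition remains, because losses in opposite directions need not cancel and the planned analysis of major failure cannot recover an event that the definition excludes.

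**Conclusion.** The point holds for one component of the primary outcome. Followed as written, Table 2 scores the same end state differently by arm when the cause is not the one named for that arm.

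A reader might go further and infer that the plan favors conventional treatment, with an odds ratio inflated by a known amount. That is not established. The gaps run in both directions, and the 1.12 to 2.25 range assumes equal true risks of 5% to 20% and losses of 10% to 50% in the conventional arm only. The loss is also applied to all major failures, although only part of one criterion is affected. These figures illustrate sensitivity and do not estimate bias; a shift of one event lies well inside sampling error. If most unrestorable teeth also have an abscess or qualifying pulpitis, the effect is small.

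The definition should still be aligned: it belongs to the primary endpoint, event counts may be low, and the remedy leaves the sample size and patient care unchanged. This is a should-fix point.

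**What to change.** Use the same third major-failure line in both columns of Table 2: *Tooth unrestorable (from caries progression, secondary caries, or loss or fracture of the restoration or crown)*. Limit the minor lines for caries progression, secondary caries, and fracture, wear or loss of the restoration to teeth that remain restorable. Record the cause on the recall CRF, if it is not already there (the forms are not in the text available), so that unrelated trauma can be identified and handled the same way in both arms.

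The cost is a small protocol amendment, brief retraining of the assessing residents, and re-scoring of failures already recorded. Section 4.2 shows that recruitment had begun, so the re-scoring should be completed before the arms are compared. No extra visits or procedures are needed. The amended third line may be less directly comparable with the published source from which Table 2 is taken.
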